Our goal is to improve PIUO beyond what has been undertaken by the child's usual clinical teams. The primary outcome is improved pain control for non-verbal children with SNI as shown in a reduction of their pain and irritability scores for the pathway group compared to the control arm for two consecutive weeks starting at week 8 or 10. Secondary outcomes include successful identification of common causes of pain and irritability in non-verbal children; decreased pain severity between baseline and the end of pathway (within 8 months post-baseline); improved family quality of life; ease of implementation of the PIUO Pathway for clinicians. We will also collect family feedback on the implementation of the PIUO Pathway.

Justification

PIUO is a source of stress for children and families. Research undertaken by our team and by others over the last fifteen years has described the manifestations of pain and irritability in children with SNI, developed assessment tools, explored its causes, and recorded the impact on families.^{5,14,18-20} With this study, we are moving forward to intervention. Many of the team members in this study are clinicians with leadership roles in programs providing care to children with SNI. Therefore findings from this study, in the form of clinical guidelines, may be rapidly translated into practice.

We have verified the importance of this research through years of focus on this issue. We developed the PIUO Pathway based on best evidence from the literature and expert opinion and performed a pilot observational study in 10 non-verbal children with SNI. The children ranged in age from 5 to 17 years and their SNI had a wide variety of causes, with high degrees of medical complexity and communication impairment. The children were recruited from community pediatric practices and all were followed by hospital sub-specialists. Our results were surprising: while it might be assumed that evaluation for pain and irritability would be thorough and revealing, just the opposite occurred in these children.³⁶ We found that:

- No child in the pilot study had been fully evaluated for PIUO before enrolling. PIUO assessment was conducted in a disorganized, scatter-shot manner, with each child receiving only partial elements of a comprehensive evaluation.

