Exclusion criteria: Children will be excluded if they are not within the specified age range; have the communication capabilities and cognitive development to localize their pain or have an explained and treatable cause of pain and irritability.

Randomization

Participants will be randomized to start the PIUO Pathway or to the waitlist control arm. The list of random allocations will be generated at WCHRI's DCC centre using REDCap. An automated audit trail of all transactions, including assigned study identification number, treatment allocation, and time and date of the transaction will be recorded by REDCap. Randomization will be stratified by site and using permuted blocks of sizes 2 and 4.

Sample Size

The sample size calculation was based on the anticipated treatment difference between PIUO Pathway arm and waitlist control arm in the period between 8 and 12 weeks. As stipulated in the section on primary outcomes (page 12) a patient will be considered a success if they are judged to be in the lowest two pain categories (A or B) on consecutive visits beginning at weeks 8 or 10. We anticipate that a 25% response to treatment during this period would be the minimal required to be viewed as clinically important, and we believe that a 25% response rate is achievable. The response rate during this period in the waitlist control is assumed to be zero, although we have set it at 5% to be cautious. To achieve 80% power using a two-tailed $\alpha=0.05$ using the Fisher's exact conditional test for comparing proportion, we require 57 patients per group. The Site Leads confirm that this number is readily obtainable within the proposed timeline.

Recruitment Procedures

It is anticipated that the same recruitment procedures will be followed at all four sites. However, minor modifications may be necessary for compliance with the individual ethics board at those institutions. Recruitment will be amongst outpatients, however if a child is hospitalized after enrolment, s/he can remain on the study.

Families will be made aware of the study via the following two channels:

1. A letter (Appendix 7) will be sent on behalf of the Principal Investigator, by the Site Leads to respective community pediatricians and sub-specialty clinics where children with SNI often receive care (e.g., Neurology, Complex Care, Orthopaedics, etc.). The letter invites them to refer patients to the study.

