- The Pain Survey tool will measure pain and irritability persistence and distress level throughout the study. A quick, two question assessment, the pain survey is taken from the Washington group Extended Question Set on Functioning (WGES-F) and is adapted here for use in children. The pain question set has been shown to have good validity and is able to correlate with other pain measurements in adults.⁵⁰ Although this two-question pain survey is simple, it is sufficiently informative so as to be of use in describing a child's pain, without unduly burdening parents with an overload of questions every two weeks. Pain Surveys will be completed biweekly throughout the Study as described below. Participants will be deemed to have had a positive outcome if they score in category A or B (see Appendix 5) on two consecutive visits. We will compare those who have a positive response on weeks 8, 10 and 12 between intervention and waitlist group.
- PROMIS-57 (Patient Reported Outcomes Measures Information System) is a multi-dimensional tool that will assess parents' well-being in the face of their child's chronic pain and irritability. This assessment is one of the two primary outcome of this project. PROMIS-57 was developed as part of an initiative of the US Department of Health and Human Services to establish a common set of patient reported outcome measures (www.healthmeasure.net). The PROMIS tools are found to be valid and reliable. There is a Canadian PROMIS coordinator as well, and support is available for translation and adaption to the REDCap database which we will be using. There are several PROMIS tools assessing various elements of adult and child health and well-being. The PROMIS-57 tool assesses across the following domains: physical function, anxiety, depression, fatigue, sleep, social participation, and pain interference in daily activity. While we cannot attribute all changes in quality of life to improvement in the child's pain and irritability, we will analyze to look for high degrees of correlation.

ANALYSIS

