The primary analytic strategy is based on the assumption that it will take some time after the screening period (weeks 0-2), the onset of randomization (week 2-3) and the Pathway initiation (weeks 4-10 in the Pathway group) for the intervention to have its full impact. As well, to determine the impact relative to the Waitlist group, the comparison must take place before the intervention is delivered to the Waitlist group (i.e. prior to cross-over). Thus, the primary analysis will focus on the measurements taken at weeks 8, 10, and 12.

The primary outcome is a change in Pain Survey score, moving a child from any high pain and irritability score (C, D, and E), to a low score (A, B) for 2 continuous reporting periods. A level B score ("little pain" on "some days") is clinically acceptable in this health challenged popula-

tion, although not ideal. Previous work has indicated that complete absence of pain is not always achievable in this population.^{3, 33}

The primary comparison will use a Fisher's exact test to compare the proportion of patients achieving a successful outcome in the period starting between week 10 and 12. We will also perform an adjusted analysis using logistic regression and treating the baseline category as a covariate.

In addition, we will compare the Pathway groups on each domain of the PROMIS-57 instrument at week 10. The dependent measures will be the domain scores at week 10, the covariates will be the scores at baseline of each domain, and the independent variable will be the Pathway group. Multiple linear regression will be used to evaluate the intervention differences. In the primary analysis, all participants measured on week 10 will be included. Multiple imputation will be used in a sensitivity analysis to include participants without measures on week 10.

As a secondary analysis, we will determine whether the intervention had an effect in the Waitlist group by comparing their measurements on the pain outcomes at week 14, 16 and 18 with their week 10 measurements (just before they cross over to the Pathway).

DATA STORAGE

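### The primary Fisher comparison is worded for a different start window (weeks 10 to 12) from the endpoint that is defined and sized (first of two surveys at week 8 or 10)

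*Protocol*

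**What the plan says.** Four places in the protocol describe the primary window consistently.

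- Objectives: lower pain scores than control "for two consecutive weeks starting at week 8 or 10".
- Sample Size: success is category A or B "on consecutive visits beginning at weeks 8 or 10". The anticipated difference is between the Pathway arm and the "waitlist control arm in the period between 8 and 12 weeks".
- Primary Outcomes: "We will compare those who have a positive response on weeks 8, 10 and 12 between intervention and waitlist group".
- ANALYSIS, first paragraph: "Thus, the primary analysis will focus on the measurements taken at weeks 8, 10, and 12".

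Later in ANALYSIS, the sentence that specifies the primary comparison has Fisher's exact test compare the proportions "achieving a successful outcome in the period starting between week 10 and 12".

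On timing, ANALYSIS states that "the comparison must take place before the intervention is delivered to the Waitlist group (i.e. prior to cross-over" and places randomization at week 2-3, after a screening period in weeks 0-2. STUDY SEQUENCE gives the waitlist ten weeks before crossover and starts the two-weekly surveys at enrolment. The secondary analysis at the end of ANALYSIS compares waitlist children "on the pain outcomes at week 14, 16 and 18 with their week 10 measurements (just before they cross over to the Pathway".

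**The concern.** The Fisher sentence uses the same kind of word (starting) as the Objectives and Sample Size sections, but attaches different weeks to it. Taken at its word, it tells the analyst to count a child whose first qualifying survey falls at week 10 or 12, not at week 8 or 10. Two analysts, each following a sentence of this protocol, could then classify the same child differently in the primary test.

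Three things are at stake. The tested endpoint would not be the one to which the assumed response rates belong. The literal window would let some waitlist successes rest on a week 14 survey taken after those children had started the Pathway. And if the wording is settled only once data are in hand, the choice of window becomes open to the charge of being made after the fact.

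**Working it through.** **1. The plan's own figure.** Inputs from Sample Size: 25% against 5%, two-sided alpha 0.05, Fisher's exact test, 80% power, 57 per group. Exact power is the sum over all i, j of Bin(i; n, 0.25) × Bin(j; n, 0.05) for those tables with Fisher p ≤ 0.05.

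| n per group | Exact power |
|---|---|
| 54 | 0.791 |
| 55 | 0.801 |
| 57 | 0.820 |
| 60 | 0.845 |

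The normal-approximation formula gives 49 without and 59 with continuity correction. So 57 holds, and 120 randomized (60 per arm if split equally) gives a little more.

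**2. Which pairs qualify.** Surveys are two-weekly, so consecutive surveys are two weeks apart.

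| Reading | Qualifying pairs |
|---|---|
| Objectives and Sample Size: first survey at week 8 or 10 | 8+10, 10+12 |
| Fisher sentence, literal: first survey at week 10 or 12 | 10+12, 12+14 |
| Fisher sentence, as weeks 10 and 12 only | 10+12 |
| Fisher sentence, as pairs completed at week 10 or 12 | 8+10, 10+12 |

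Only the last reading agrees with the sized endpoint, and it requires taking starting to mean ending.

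**3. Where the definitions differ.** Write 1 for A/B and 0 otherwise at weeks 8, 10, 12, 14, which gives 2^4 = 16 patterns.

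- Sized success needs week 10 = 1 and at least one of weeks 8 and 12 = 1: 3 × 2 = 6 patterns.
- Literal success needs week 12 = 1 and at least one of weeks 10 and 14 = 1: 3 × 2 = 6 patterns.
- Sized only: 1100 and 1101. Literal only: 0011 and 1011. They disagree on 4 of 16.
- Under the 10+12-only reading there is 1 disagreement (110) among the 8 patterns over weeks 8, 10 and 12.

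These counts show which kinds of children are affected. They are unweighted and do not say how many children there would be.

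**4. Power under the literal window.** The protocol gives no rates for it. Purely as assumed examples at 57 per group, 20% against 5% gives 0.59, 25% against 10% gives 0.47 and 30% against 10% gives 0.71. They show only that 80% power does not carry over automatically to an endpoint with other rates. They are not estimates of the loss.

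**5. The crossover clock.**

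- Counting from enrolment, with randomization at week 2-3: 2 + 10 = 12 and 3 + 10 = 13, so crossover falls at week 12-13. Week 10 is then not immediately before crossover.
- Counting from randomization: 0 + 10 = 10, so crossover falls at week 10. The week 12 survey, which asks about the preceding two weeks, then lies wholly after crossover, against the rule in ANALYSIS.

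Neither clock satisfies every statement. For the sized endpoint, the week 12 survey decides the result only for a child who is not A/B at week 8 but is A/B at week 10 (1 of the 4 week 8/week 10 patterns). Each such waitlist child can move the control proportion by at most 1/57 = 1.8 percentage points.

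**The case against.** The best defence is that the document largely corrects itself. The opening of ANALYSIS confines the primary analysis to weeks 8, 10 and 12 and requires it to precede crossover, which argues against any use of week 14. Sample Size also names Fisher's test and ties it to the week 8 or 10 start, so the disputed sentence is not the only guide. Four consistent statements stand against one loose one, and reading the sentence as pairs completed at week 10 or 12 removes the conflict entirely.

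Much of this stands. A slip is the likely explanation, and a careful analyst would probably not use 12+14. But the sentence is the one in ANALYSIS that says what the primary test compares, and it agrees with the definition only if a word is read as its opposite. Dropping the week 12+14 pair does not cure it either: what remains is 10+12 alone, which still loses 8+10.

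On the crossover, the defence is stronger. Only one numbered week is tied to crossover in the text. Week 12-13 is an inference from two sections. On that clock the week 8, 10 and 12 set and the later weeks 14, 16 and 18 fit well enough, and only the remark about week 10 is loose. The schedule is in Appendix 1, 1a and 1b, which were not available here and may settle it.

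A reader might go further and infer that the sample size is wrong, that the trial is underpowered by some stated amount, or that waitlist contamination is built into the primary analysis. The documents support none of these. The 57 reproduces, no rates are given for the other window, and whether week 12 precedes crossover cannot be decided from the body text.

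**Conclusion.** The point holds as a contradiction in the wording of the primary comparison. The Fisher sentence does not match the endpoint defined in Objectives and sized in Sample Size, nor the weeks listed in Primary Outcomes and in ANALYSIS itself. Literally applied, it loses children who are A/B at weeks 8 and 10 but not 12, and gains children who are A/B at weeks 12 and 14 but not 10. How many children that is, and what it does to power, cannot be derived from the protocol. It should be corrected before analysis because it decides who counts as a success in the primary test.

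This rests on surveys being two-weekly, as stated, and on the word starting referring to the first of the two surveys, as it does in Objectives.

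The crossover timing is a separate and less certain matter: the body text does not fit one clock, but the appendices may resolve it.

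**What to change.** 1. In ANALYSIS, replace the period phrase in the Fisher sentence with: *moving from category C, D or E at baseline to A or B on two consecutive biweekly surveys, the first at week 8 or week 10*. This keeps the starting-category condition that ANALYSIS already sets. The sponsor should confirm that baseline is the intended reference.
2. Use the same definition in Objectives (which now speaks of two consecutive weeks although surveys are two weeks apart), Sample Size and Primary Outcomes.
3. Reconcile STUDY SEQUENCE and ANALYSIS on one clock that states week 0, the week of randomization and the crossover week, in line with Appendix 1. Confirm that every survey used in the primary endpoint precedes crossover.

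The cost is wording only. The surveys are already scheduled, no data are added, and 57 per group stays as it is because it was sized on this endpoint.

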Interventions for resolving PIUO are time and resource intensive. They require a focused approach to assessing all the underlying possibilities for the PIUO and addressing each potential source of pain one at a time. Tackling PIUO requires systematic, comprehensive, process-oriented thinking applied by an interdisciplinary team with flexibility in terms of approach and time. There have been recommendations in the literature about how to approach the problem of PIUO in children with SNI, but these recommendations have never been subjected to systemic evaluation as complex interventions, for example by following an integrated clinical pathway.^{12,37} Integrated clinical pathways (also called "care pathways" or "critical pathways") are structured, sequenced approaches guiding the delivery of healthcare, often with a multidisciplinary perspective.³⁸ They provide algorithms to be followed in the assessment and treatment of conditions, but are not intended to be rigidly followed; instead, integrated clinical pathways delineate a foundation for a clinician's approach to a complex problem, thereby avoiding inefficiencies in evaluation or resource use. Integrated clinical pathways are a form of Complex Interventions and have been developed for sickle cell pain,³⁹ childhood asthma,⁴⁰ appendicitis,⁴¹ autoimmune conditions,⁴² inborn errors of metabolism,⁴³ and cerebrospinal fluid shunt management.⁴⁴ Despite their complexity, integrated clinical pathways are appropriate interventions for evaluation by Randomized Controlled Trial (RCT).⁴⁵ RCTs of integrated clinical pathways have been proposed and/or completed for complex, multi-factorial patient problems including lung disease, heart failure, gastrointestinal surgery, stroke, and hip fractures.^{38,46-48}

In this study, we will use a waitlist-controlled RCT design, with 120 children randomized to PIUO Pathway or waitlist (standard care) treatment arms. This design was chosen strategically, with consideration of both the special pediatric population being studied and the ethical inappropriateness of randomly assigning children to a placebo group when pain is the target condition.

The Study Sequence, Events Grid and a detailed depiction of the PIUO Pathway are shown in Appendix 1, 1a and 1b.

STUDY SITES

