In order to use an RCT to assess the effectiveness of the PIUO Pathway, we need a large number of participants - more than can be found in one center. Therefore, with the help of colleagues we will recruit children from across Canada into the study. Children will be recruited at 4 participating centers where Site Leads familiar with our population and the issue of PIUO are located: BC Children's Hospital (BCCH), Vancouver ([name]), Alberta Children's Hospital (ACH), Calgary ([name]), Hospital for Sick Children (HSC), Toronto ([name]) and Children's Hospital of Eastern Ontario (CHEO), Ottawa ([name]).

RECRUITMENT

Participants

Children aged 6 months to 18 years with SNI (from any cause) with unexplained pain and irritability and whose cognitive or communication impairments prevent determination of pain location, cause, and type will be eligible to participate.

Eligibility

Inclusion criteria: Eligible children will have cognitive impairment or be non-verbal and have severe levels of disability equivalent to Gross Motor Functional Classification System (GMFCS) scores of 3, 4 or 5. Eligible children will score ≥ 3 on two scales administered via an Eligibility Screening (Appendix 2) that measure persistence and distress level the child is experiencing as well as identifies the type of pain and irritability as PIUO – with no obvious cause or explanation. The score of ≥ 3 on the scale measuring pain persistence and distress level confirms that the child is experiencing pain and irritability more than “a little” on “some days”. The parent will confirm that the experience of pain and irritability has been present within the last month of the eligibility screening, although we recognize that some children will have experienced PIUO for much longer. The score of ≥ 3 on the pain identification scale indicates that the child has unexplained pain and irritability (as opposed to, for example, ongoing pain due to a known cause such as esophagitis). Parents should have sufficient English/French language skill, or have access to assistance, to participate in the clinic visits and complete survey tools. The Child will also have a score of 4 or 5 on the Communication Function Classification System (CFCS).

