In Step 1, any information gained may then lead to directed testing with imaging or laboratory studies. As an example of directed testing, if the child has pain with transfers into a wheelchair the physician may order an x-ray to rule out hip dislocation. Any findings from directed testing (or screening testing as described below) will be shared with the child's usual care team (i.e. primary team) via the standard reporting system available at each study site (paper and/or electronic record). Findings related to pain sources will be managed by the Site Lead clinician, whereas incidental findings will be referred for management by the child's usual care team.

If Step 1 is unrevealing, **Step 2** consists of a series of screening tests. The screening tests are designed to look for sources of pain that would not necessarily be revealed in a careful Hx&PE or directed testing. If any screening test has already been completed within 6 months prior to the participant enrolling in the PIUO Pathway, it is not repeated, unless the pain and irritability symptoms have changed since the test was done. The exception is the Hx&PE, which is always done at the Step 1 visit by the study team. The utility of the step approach is provided by a study that used directed tests and screening to assess PIUO in a limited and more expensive workup with nuclear medicine imaging.⁵²

The 4 PIUO standard screening tests are:

1. Urinalysis
2. Ultrasound - abdominal
3. Gastric pH (if G-tube present)
4. Bloodwork , including:
 - i. Complete Blood Count/CBC - White blood cells/WBC, Hemoglobin/Hgb, Hematocrit/Hct
 - ii. Alkaline Phosphatase/Alk Phos
 - iii. Alanine Aminotransferase/ALT

- iv. Aspartate Aminotransferase/AST
- v. Bilirubin
- vi. C reactive protein/CRP
- vii. Creatinine/Cr
- viii. Electrolytes – Sodium/Na, Potassium/K, Calcium/Ca, Magnesium/Mg, Chloride/Cl and Phosphorus/PO4
- ix. Ferritin
- x. Gamma Glutamyl Transpeptidase/GGT
- xi. Immunoglobulin A/IgA
- xii. Lipase
- xiii. Anti-endomysial antibodies/TTG

Although the above screens are standard of care, the order of these tests (e.g. performing Hx & PE) then Step 1 tests, and then moving to Step 2 screens is a novel approach being tested here. If Step 2 imaging or exams were required as part of Step 1, then they will not be repeated at Step 2.

DATA COLLECTION TOOLS

All Instruments to be used for data collection will be available in English and French or an interpreter will be available when the tool is used:

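### Randomization is stratified by site but neither adjusted model includes site, and ordinary logistic regression gives no usable odds ratio if no waitlist child succeeds

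*Protocol*

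**What the plan says.** - **Randomization (Protocol, Randomization):** "Randomization will be stratified by site and using permuted blocks of sizes 2 and 4". No other stratification factor is named. Study Sites lists four centres ("Children will be recruited at 4 participating centers") and Study Design gives the total ("with 120 children randomized to PIUO Pathway or waitlist (standard care) treatment arms").
- **Delivery of the intervention (Protocol, The PIUO Pathway):** "Findings related to pain sources will be managed by the Site Lead clinician". Part of the treatment therefore depends on who leads the site.
- **Adjusted binary analysis (Protocol, Analysis):** "We will also perform an adjusted analysis using logistic regression and treating the baseline category as a covariate". This supports a primary Fisher's exact test, which is not stratified.
- **PROMIS-57 at week 10 (Protocol, Analysis):** "the covariates will be the scores at baseline of each domain, and the independent variable will be the Pathway group". Under Primary Outcomes the Protocol says of PROMIS-57: "This assessment is one of the two primary outcome of this project".
- **Expected waitlist response (Protocol, Sample Size):** the rate in the "waitlist control is assumed to be zero, although we have set it at 5% to be cautious". The Pathway rate is taken as 25%.

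Site is not named as an analysis term anywhere in the Protocol, and no method is given for an arm with no successes.

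**The concern.** There are two linked faults in how the adjusted models are fixed.

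**Site is left out.** When allocation is balanced within sites and outcomes differ between sites, a model without site leaves the between-site variation in the residual. The standard error of the treatment effect is then too large for the design, so the test is conservative and some power is lost. The analysis also fails to follow the groups within which children were randomized. Since each Site Lead manages the pain findings, differences between sites are plausible.

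**The logistic model can break down under the plan's own expectation.** If no waitlist child succeeds, the treatment coefficient has no finite maximum-likelihood value. Software then reports a huge odds ratio with a huge standard error and a Wald p value near 1, next to a Fisher p value far below 0.001. The adjusted odds ratio and its usual interval could not be reported, and the replacement method would have to be chosen after the data were seen.

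**Working it through.** **1. The plan's own figure.** Inputs from Sample Size: 25% vs 5%, two-sided 0.05, 80% power, Fisher's exact test, 57 per group. Summing the two binomial distributions over all tables with Fisher p ≤ 0.05 gives power 82.0% at 57 and 84.5% at 60 per arm. The smallest adequate size is 55 (80.1%), so 57 suffices. At 60 per arm the actual size of the test is 1.0% when both rates are 5% and 2.7% when both are 15%. The primary test is valid and conservative and has its stated power, so no error is claimed there.

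**2. Chance of no waitlist success.** P = (1 − p)^n.

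| True waitlist rate | n = 57 | n = 60 |
|---|---|---|
| 5% | 0.95^57 = 5.4% | 0.95^60 = 4.6% |
| 2% | 0.98^57 = 32% | 0.98^60 = 30% |
| 0% | 100% | 100% |

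**3. What the methods return at 15/60 vs 0/60** (25% against none, two-by-two table).

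| Method | Result |
|---|---|
| Fisher | p = 0.000022 |
| Ordinary logistic, Wald | log-odds 23.5, SE 16,913, p = 0.999 |
| Ordinary logistic, likelihood ratio | 22.9 on 1 df, p = 0.000002; profile lower bound for the odds ratio 9.4, no upper bound |
| Firth logistic | OR = (15.5/45.5)/(0.5/60.5) = 41; profile 95% CI 5.3 to 5,312; p = 0.000008 |

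The data are not the problem: only the Wald output and the point estimate fail.

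**4. Would adding site to the ordinary model do?** Simulation with 60 per arm, 25% vs 5%, 1,500 replicates per row. The table shows how often at least one coefficient is infinite. Site and category shares are assumptions; the Protocol gives none.

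| Sites / baseline categories | Without site | With site |
|---|---|---|
| equal / equal | 4.9% | 6.7% |
| 40/30/20/10 / equal | 5.1% | 19.7% |
| equal / 60/30/10 | 20.3% | 21.3% |
| 40/30/20/10 / 60/30/10 | 19.9% | 31.3% |

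The arm coefficient itself is infinite in 4 to 5% of replicates throughout. Adding site without penalisation therefore makes separation more likely.

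A Firth model with arm, site and category rejects a true null 4.1% of the time at a 5% rate and 4.4% at 15%. With a site standard deviation of 1 on the log-odds scale it rejects 2.7% at 5%. Its power at 25% vs 5% is 90.1% with no site differences and 87.7% with that standard deviation.

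**5. PROMIS-57 regression with and without site.** 120 children, 4 sites, ordinary least squares, 6,000 replicates. The ICC is the assumed residual share of variance between sites.

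| ICC | Type I without / with site | Power without / with site |
|---|---|---|
| 0.05 | 4.7% / 5.1% | 80.2% / 81.2% |
| 0.10 | 4.5% / 5.4% | 80.5% / 82.9% |
| 0.20 | 3.7% / 5.3% | 83.1% / 87.5% |

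At ICC 0 adding site costs nothing measurable. Other runs of this set-up, with 112 or 120 children, gave 3.1% to 3.4% without site at ICC 0.20, so the direction is stable.

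**The case against.** **This belongs in the SAP.** The choice of estimator, the handling of separation and the stratification terms of a supportive model are often left to the SAP, which is not shown. The logistic sentence does not say that baseline category is the only covariate or that maximum likelihood with Wald inference will be used. This has some force for the logistic model. It has little for PROMIS-57, where the Protocol itself sets out the outcome, the covariates and the independent variable.

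**The site effect is small and rests on assumed ICCs.** This stands in part. With 6,000 replicates the Monte Carlo standard error near 5% is √(0.05 × 0.95 / 6,000) = 0.28 percentage points, so 4.7% at ICC 0.05 cannot be told from 5%. The loss is clear only if sites differ substantially. The direction is conservative, so no false claim results.

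**PROMIS-57 may not be primary.** The Objectives list family quality of life as secondary, against the statement under Primary Outcomes. Its status is contradictory and should not be used to raise the grade of this point.

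**The empty arm is unlikely at the design rate and does little harm.** At 5% the chance is about 1 in 20. The Fisher result would stand, the likelihood-ratio test would work, and the Firth upper limit would be very wide. All true. But zero is the rate the Protocol says it expects, and at 2% the chance is already near one in three.

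**Site in a sparse logistic model is itself risky.** This is correct for ordinary maximum likelihood, and it is why the remedy pairs site with penalisation.

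**Conclusion.** The point holds and should be corrected, at moderate weight. The Protocol randomizes within site and then specifies adjusted models without it. For PROMIS-57 the consequence is loss of efficiency, not bias: about 1, 2 and 4 power points at ICCs of 0.05, 0.10 and 0.20, and none at 0. For the logistic model, ordinary maximum likelihood gives no reportable odds ratio or Wald interval when the waitlist arm has no success. At 57 or 60 per arm that has a chance of about 5% at the sizing rate, about 30% at a 2% rate, and certainty at the rate the Protocol assumes.

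The primary Fisher test, its conclusion and the sample size are not affected. The empty-arm probabilities depend only on the arm size and the true rate. The site results depend on assumed ICCs, site shares and category shares.

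**What to change.** - **Primary test:** keep Fisher's exact test, which matches the basis of the sample size.
- **Adjusted binary analysis:** replace the sentence with wording such as: *An adjusted analysis will use Firth-penalised logistic regression with treatment arm, site and baseline Pain Survey category, reporting penalised likelihood-ratio tests and profile-likelihood intervals.* Exact logistic regression is an alternative. Site should not simply be added to an ordinary maximum-likelihood fit.
- **PROMIS-57:** add site as a covariate in each domain regression.
- **Optional sensitivity analysis:** a Cochran-Mantel-Haenszel test stratified by site. With no site differences its simulated power is 89.0% at 57 and 89.3% at 60 per arm, against 82.2% and 84.3% for Fisher in the same simulation. Most of that gain comes from avoiding Fisher's conservatism, not from site.

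**Cost:** two sentences and a few lines of code; site is already recorded for randomization. The downside is a crowded supportive model. It has 1 arm, 3 site and 2 category terms, so 6 terms on about 60 × 0.25 + 60 × 0.05 = 18 expected events. If no waitlist child succeeds, even the Firth upper limit stays very wide.
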